7.8. SAE Reporting to KCI

SAEs will be reported via the KCI SAE Report Form. This form should be completed by the Investigator, or designee, and submitted (fax or email) to KCI within 24 hours of the Investigator becoming aware of the event. The KCI SAE line is available for SAE reporting 24 hours per day and is monitored during normal business hours.

7.9. UADE Reporting - Unanticipated Adverse Device Effect (UADE)

A UADE is any **SAE** on health or safety or any life-threatening problem or death caused by, or associated with, a device, if that effect, problem, or death was not previously identified in nature, severity, or degree of incidence in the investigational plan or

application (including a supplementary plan or application), or any other unanticipated serious problem associated with a device that relates to the rights, safety, or welfare of subjects. (21 CFR 812.3)

The Sponsor (KCI) will immediately conduct an evaluation of the received SAEs to determine whether the event meets the UADE definition. If the event is determined to be an UADE, KCI will report the results of the evaluation to FDA, and participating Investigators.

If KCI determines that the event presents an unreasonable risk to the study subjects, it will terminate all clinical studies or parts of studies presenting risk as soon as possible.

7.10. Follow-up Period for Ongoing AEs

Treatment-related AEs (serious and non-serious) which are ongoing at the final study visit will be followed until resolution or stabilization. All other adverse events will be considered closed (outcome = “ongoing”) at the time the subject completes participation in the study.

8. STATISTICAL CONSIDERATIONS

8.1. Endpoint Definitions for Analysis

8.1.1. Primary Endpoint – Subject Incidence SSC

The primary endpoint is the incidence of surgical site complications (SSCs) within 90 days of TKA revision in subjects treated with ciNPT as compared to standard of care surgical dressing. The SSC endpoint includes any occurrence of superficial SSI, deep SSI, dehiscence, seroma, hematoma, skin necrosis, or continued drainage as outlined in section 4.11.1. For this endpoint there are three possible outcomes:

- “Occurred”, which is assigned if the subject had one or more occurrences of any complication and the onset date of the complication was between the time of the TKA revision and not later than 90 days after;
- “No occurrences”, which is assigned if the subject had no known occurrences of a complication within 90 days of the TKA revision and was assessed at least once on or after the 90th day following the TKA revision;
- “Incomplete follow-up”, which is assigned if the subject had no occurrences of the complication within 90 days of the TKA revision and did not have an assessment at least 90 days after the date of the revision surgery.

If a subject experiences one occurrence of any of the six complications, the primary outcome will be considered “Occurred”.

For each component of the SSC, the start date of the complication will be recorded in order to calculate the number of days from the revision surgery until occurrence of the event. If the complication did not occur, the number of days will be calculated using the last assessment which confirmed the subject to be complication-free.

8.1.2. Secondary Endpoints

8.1.2.1. Subject Incidence SSI

This secondary endpoint is the incidence of any SSI (superficial or deep) within 90 days of TKA revision in subjects treated with ciNPT as compared to SOC dressing. Superficial SSI is a component of the primary endpoint and specific instructions for ascertainment are described in sections 4.11.1. Subjects will be categorized using methods similar to those described in section 8.1.1.

8.1.2.2. Subject Incidence Deep SSI

This secondary endpoint is the incidence of deep SSI within 90 days of TKA revision in subjects treated with ciNPT as compared to SOC dressing. Deep SSI is a component of the primary endpoint and specific instructions for ascertainment are described in section 4.11.1. Subjects will be categorized using methods similar to those described in section 8.1.1.

8.1.3. Exploratory Endpoints

8.1.3.1. Pain Assessment

The pain assessment consists of two self-administered questions used to evaluate the severity of a subject's pain in the past 24 hours. Both questions are measured from 0 (no pain) to 10 (pain as bad as you can imagine).

Subjects will respond using the integer value. Subjects who have withdrawn prior to the scheduled assessments will be categorized as "Discontinued study prior to assessment"; otherwise subjects who do not have an assessment recorded at a particular visit will be summarized as "Assessment not done".

8.1.3.2. Knee Injury and Osteoarthritis Outcome Subscale Score (KOOS)

The KOOS instrument is a patient-reported questionnaire to assess short-term and long-term symptoms and functions.

The KOOS consists of 42 items asked on a 5-point Likert scale. The items will be converted to numeric values and summarized into five domain scores: Knee-Related Quality of Life, Function in Sport and Recreation, Function in Daily Living, Pain, and Other Symptoms. The subscales are scored separately and interpreted separately. Each subscale score will be normalized from 0 (extreme symptoms) to 100 (no symptoms).

All efforts will be made to ensure the subjects complete the entire assessment at each scheduled visit. Each subscale will be scored using the most recent KOOS Users Guide and Scoring Instruction manuals which outline methods for imputing missing data.^{18;19}

For the subscale scores, four possible outcomes will be summarized and listed:

- Normalized numeric subscale score;
- Assessment done but incomplete (sufficient number of items not complete);
- Discontinued study prior to assessment;
- Assessment not done

8.1.3.3. Patient-Reported Outcomes Measurement Information System (PROMIS) Global-10

The PROMIS Global-10 is a generic health assessment that measures the physical, social, and emotional health of individuals and is often used for those living with chronic conditions. All efforts will be made to ensure the subject completes the entire assessment, which consists of 10 questions, at each scheduled visit.

Two domains will be scored separately and each will be interpreted separately: Global Physical Health and Global Mental Health. For each subscale, there are three possible outcomes:

- Raw numeric subscale score and converted t-score;
- Assessment done but incomplete (sufficient number of items not complete);
- Discontinued study prior to assessment;
- Assessment not done.

8.1.3.4. 30-Day Subject Incidence of SSC

This endpoint is the incidence of the SSC within 30 Days post TKA revision in subjects treated with ciNPT as compared to SOC dressing. Section 4.11.1 describes the methods for ascertaining surgical site complications. Subject outcomes will be categorized using methods similar to those described in section 8.1.1.

8.1.3.5. 45-Day Subject Incidence of SSC

This endpoint is the incidence of the SSC within 45 Days post TKA revision in subjects treated with ciNPT as compared to SOC dressing. Section 4.11.1 describes the methods for ascertaining surgical site complications. Subject outcomes will be categorized using methods similar to those described in section 8.1.1.

8.1.3.6. Safety Endpoint

Adverse events will be coded using the MedDRA dictionary. Treatment-emergent adverse events (TEAE) are those which first appear or worsen after the application of the study treatment. Subject incidence of TEAEs will be summarized by system organ class and preferred term by treatment group.

All adverse events occurring during the study will be listed by subject in data listings.

8.2. Analysis Sets

The following analysis sets will be used:

- ITT Analysis Set – The ITT (intention-to-treat) Analysis Set will consist of all randomized subjects. Subjects will be analyzed according to the treatment allocated at randomization.
- Safety Analysis Set – The Safety Analysis Set will consist of all randomized subjects who received any study-related treatment procedures. It is expected that all randomized subjects will be treated. All safety results will be presented based on the Safety Analysis Set. Subjects will be analyzed according to the study treatment they received immediately following the TKA revision.
- Modified ITT (mITT) Analysis Set – This set will include subjects in the ITT Analysis Set with the following: 1) an SSC on or before 90 days post-TKA revision or 2) no known occurrence of an SSC within 90 days of the TKA revision and was assessed at least once on or after the 90th day following the TKA revision. Subjects will be analyzed according to their randomized treatment assignment.
- Per-Protocol Analysis Set – This will include subjects in the mITT Analysis Set and had no disqualifying protocol deviation(s) that would impact the interpretation of the primary endpoint. The disqualifying protocol deviation(s) for exclusion from this set will be defined and documented in a blinded fashion prior to the final database lock by the Protocol Deviation Review Committee. Subjects will be analyzed according to their randomized treatment assignment.
- Modified Per-Protocol (mPP) Analysis Set – This will include subjects in the Per-Protocol Analysis Set excluding any subjects that received prohibited therapy as described in section 4.15 or any subjects that received alternative therapy following the study treatment period.

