4.4. Subject Withdrawal or Termination

4.4.1. *Reasons for Withdrawal or Termination*

Subjects may withdraw from participation in the study at any time upon request.

The Investigator may choose to terminate participation of the subject from the study with or without their consent for any of the following reasons:

- Adverse events
- Noncompliance
- For any reason that may, in the opinion of the Investigator, negatively affect the safety or well-being of the subject.

An Investigator must terminate participation of a subject from the study for any of the reasons indicated in section 4.15.

4.4.2. *Handling of Withdrawal or Termination*

Every effort should be made to assess SSCs and adverse events prior to the subject withdrawal. If a subject does not return for a scheduled visit, every effort should be made to contact the subject.

For subjects who are lost to follow-up, the Investigator will make attempts to collect at least the vital status (e.g., whether the subject is alive) before formally withdrawing the subject from the study. Prior to considering a subject lost to follow-up at least two documented attempts should be made to contact the subject through all available routes, and a certified letter should be sent to the permanent address on file.

Once the subject withdraws from the study, no further study evaluations will be performed, and no additional data will be collected. The Investigator may retain and continue to use any data collected before withdrawal. The subject will not be replaced.

If for any reason the subject is withdrawn by the Investigator from this study, the Investigator will inform the subject and KCI.

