4.10.3.3. Documentation

The following information regarding the application of study treatments will be documented after the surgery:

- Date of removal
- SOC only
- The number of dressing replacements
- Type of dressing (if any) applied after removal of study treatment
- ciNPT only
- Replacement of therapy unit
- Number and dates of dressing replacements (Prevena™ Peel & Place™ or Prevena Plus™ Customizable™)
- Type of dressing (if any) applied after removal of ciNPT

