4.11.2. Intervention Assessment

Information related to all interventions that are performed for an SSC will be documented at all post-surgery visits including unscheduled visits. Information collected will include but is not limited to:

- Date of intervention
- Type of interventions
- Types of interventions may include open surgical or percutaneous drainage, debridement, excision, or re-operation.

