4.15. Prohibited Procedures and Treatments

Subjects who undergo a subsequent surgery involving the initial TKA incision within 90 days must withdraw from the study.

Subjects who receive a subsequent TKA revision on the same knee within 90 days of the study revision must withdraw from the study prior to the procedure. Sites will record any SSCs that occur prior to the subsequent TKA revision and document the revision as the reason for the withdrawal from the study.

In the absence of an SSC, subjects receiving cross-over therapy after completing the original study treatment (ie, therapy from the arm in which the subject was not initially treated) must withdraw from the study.

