7.7. AE Collection/Reporting Period

The AE collection/reporting period will begin after the subject has been randomized. Investigators should assess for AEs at each visit. In addition, study subjects should be instructed to report any AE that they experience to the Investigator.

All AEs, regardless of perceived relationship to study product, will be reported and recorded on the appropriate CRFs in a timely manner. In addition, the worsening of a medical condition previously reported in the medical history should also be recorded as an AE.

The reporting of all AEs is to continue for the duration of the study or until the patient receives an alternative therapy, whichever occurs first. Any SAE that occurs after treatment with alternative therapy is to be reported only if the Investigator or treating physician assesses the SAE as related to the study treatment.

The AE description will include the nature of the experience (AE term), the start date, the end date, the severity of each sign or symptom, the seriousness of the event or experience, relationship to study treatment, the course of action taken, and the outcome of the experience. Indicate if the AE caused the subject to be discontinued from the study.

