8 STATISTICAL ANALYSES OF EFFICACY MEASURES

8.1 Subject Enrollment and Disposition

Summaries in this section, section 8.1, will be based on all subjects who provided informed consent. The summary of enrollment and subject disposition will include:

- All screened subjects who provided informed consent
- All randomized subjects – ITT analysis set (overall and by revision type)
- In ITT analysis set: All subjects who completed and discontinued from the study along with their reasons for discontinuation
- All randomized and treated subjects – Safety analysis set
- All subjects in mITT, PP, mPP and Safety analysis sets (overall and by revision type)

Additionally, figure(s) may be generated to display the enrollment and disposition summary graphically.

Summaries for all screen failure subjects or subjects excluded from any analysis sets will be provided as well. The summaries will include:

- All screen failure subjects along with the reason for failing screening
- All subjects excluded from mITT analysis set along with the reason for exclusion
- All subjects excluded from PP analysis set along with the reason for exclusion
- All subjects excluded from mPP analysis set along with the reason for exclusion
- All subjects excluded from Safety analysis set along with the reason for exclusion

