8.5.1 Additional Analyses of Primary Endpoint

The below additional analyses (identified as sensitivity analyses in tables) described below may be performed for the primary efficacy endpoint, SSC:

- The primary analysis will be repeated using the actual revision type.
- A CMH test for SSCs stratified by randomized and actual revision type for the ITT, PP, and mPP will be included. Odds ratios and 95% confidence intervals will be presented.
- Summary of SSC events by type which include superficial SSI, deep SSI, dehiscence, seroma, hematoma, skin necrosis, or continued drainage based on the ITT, mITT, PP, and mPP analysis sets. Additionally, we will include SSC events of continued drainage that developed into SSIs.
- Summarize SSC events required intervention by type which include superficial SSI, deep SSI, dehiscence, seroma, hematoma, skin necrosis, and continued drainage based on the ITT, mITT, PP, and mPP analysis sets.
- For the septic and aseptic subpopulations, a Chi-square or Fisher's test as appropriate, will be performed within each actual revision type for SSC incidence rates between treatment groups based on the corresponding septic and aseptic mITT analysis sets.
- Perform a Fisher's exact test or Chi-square to compare the SSC incidence rates between two treatment arms without revision type stratification based on the mITT analysis.
- Multivariable analyses comparing the treatment groups with covariate adjustment where possible covariates might include (but not limited to) site, age, BMI, sex, type of revision (aseptic or septic), and subject comorbidities using logistic regression based on the mITT.

- Analyses comparing the heterogeneity of the treatment groups across clinical sites using logistic regression. (CMH) test stratified by clinical site based on the mITT.

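### The mPP set drops subjects for alternative therapy even when it followed an SSC; for cross-over therapy that can remove only primary events and distort an optional sensitivity analysis

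*Protocol*

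**What the plan says.** The analysis sets are nested: mPP lies within Per-Protocol, and Per-Protocol within mITT (Protocol 8.2, SAP 5). An SSC-free subject enters mITT only with an SSC assessment on or after Day 90; a subject with an SSC by Day 90 enters whatever happens later. mPP then drops those who had prohibited therapy under Protocol 4.15, or "any subjects that received alternative therapy following the study treatment period".

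Protocol 4.15 does distinguish cross-over before an SSC from cross-over after one. Its withdrawal rule covers "In the absence of an SSC, subjects receiving cross-over therapy after completing the original study treatment". After withdrawal, "no further study evaluations will be performed, and no additional data will be collected" (Protocol 4.4.2). Subjects with a documented SSC stay under assessment (Protocol 4.11.1).

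On use, SAP 8.5.1 says of its sensitivity analyses: "A CMH test for SSCs stratified by randomized and actual revision type for the ITT, PP, and mPP will be included". The lead-in to that section makes the whole list optional. SAP 8.5 and 8.6 also summarise SSC, SSI and deep SSI on mPP. SAP 8.1 will report "All subjects excluded from mPP analysis set along with the reason for exclusion".

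Neither document defines alternative therapy. Protocol 7.7 uses the term for the end of AE reporting ("until the patient receives an alternative therapy, whichever occurs first") without saying what it covers.

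**The concern.** A per-protocol exclusion should remove subjects whose treatment could have altered the outcome. Therapy that starts after a first SSC cannot have caused or prevented that SSC, and the subject's primary outcome is already fixed as an event. Removing the subject for it is selection on care given after the outcome. The trial is open-label, so that care is chosen by an investigator who knows the arm, and nothing in the plan makes the share of events so treated equal between arms.

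At stake is the mPP CMH test and the mPP summaries. A sensitivity analysis that deletes events because they were treated is a poor check on whether the mITT result is robust.

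**Working it through.** **Step 1: who can be removed for cross-over before Day 90, if 4.15 is followed?**

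- No SSC: must withdraw (4.15), no further data (4.4.2), so no Day 90 assessment. The subject counts as incomplete follow-up and is outside mITT, PP and mPP already. The mPP rule has nothing left to remove.
- SSC first, then cross-over: not required to withdraw, counted as an event, in mITT and (absent another deviation) in PP. The mPP rule removes this subject.

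So this limb acts on events only. The withdrawal rules for repeat surgery in 4.15 can act in the same way through the prohibited-therapy limb, because re-operation may itself be treatment for an SSC (Protocol 4.11.2).

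**Step 2: reproduce the planned sample size.** Inputs from Protocol 8.4.2: 20% vs 10%, two-sided 0.05, 80% power.

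n = [1.960·√(2·0.15·0.85) + 0.842·√(0.20·0.80 + 0.10·0.90)]² / 0.10² = (0.990 + 0.421)² / 0.01 ≈ 199 per arm, as stated.

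**Step 3: effect on the estimates.** Let q be the share of SSC subjects dropped. No q is given in the documents; 10% and 25% are assumptions.

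- Rate after exclusion: p(1−q)/(1−pq). For p = 0.20, q = 0.25: 0.15/0.95 = 15.8%. For p = 0.10, q = 0.25: 0.075/0.975 = 7.7%.
- Odds ratio after exclusion: OR × (1−q_ciNPT)/(1−q_SOC), with planned OR = (0.10/0.90)/(0.20/0.80) = 0.444.

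Power is from a simulated CMH test: 200,000 trials, 100 septic and 99 aseptic per arm, SOC 33% and 6.9%, ciNPT half of each, two-sided 0.048.

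| q ciNPT / q SOC | ciNPT | SOC | Difference (points) | OR | Power |
|---|---|---|---|---|---|
| 0 / 0 | 10.0% | 20.0% | 10.0 | 0.444 | 83.3% |
| 10% / 10% | 9.1% | 18.4% | 9.3 | 0.444 | 79.8% |
| 25% / 25% | 7.7% | 15.8% | 8.1 | 0.444 | 73.9% |
| 25% / 10% | 7.7% | 18.4% | 10.7 | 0.370 | 90.6% |
| 10% / 25% | 9.1% | 15.8% | 6.7 | 0.533 | 56.8% |

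The counts behind this are small: at q = 25%, 199 × 0.10 × 0.25 ≈ 5 ciNPT and 199 × 0.20 × 0.25 ≈ 10 SOC subjects.

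**Step 4: no true effect** (33% and 6.9% in both arms). With no exclusions, 2.4% of trials give a significant result in favour of a given arm. With 25% of events dropped in one arm and 10% in the other, 9.0% favour the arm that lost more events.

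**Step 5: if the term is broader.** If non-events are dropped too, at share r, the odds ratio is also multiplied by (1−r_SOC)/(1−r_ciNPT). With r at a quarter, half or all of the event shares in Step 4, the 9.0% falls to 6.9%, 5.0% and 2.4%.

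**The case against.** No conclusion rests on mPP. The primary and secondary tests use mITT, the mPP test is one optional sensitivity analysis shown beside ITT and PP, and exclusions will be listed with reasons. This stands and keeps the point minor. Listing shows the loss, but it does not correct the mPP estimate.

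The events-only result is also narrow. Protocol 4.10.3.3 records later dressings in both arms (for one arm, "Type of dressing (if any) applied after removal of ciNPT"), so a broad reading of alternative therapy would remove non-events as well. Protocol 3.2 says subjects are followed for 90 days whatever treatment they received, which a site might apply instead of 4.15. A cross-over first disclosed at the Day 90 visit may already have its Day 90 assessment. And NPWT given to an SOC subject might be judged a disqualifying deviation, so that the subject leaves PP first. All of this stands; the point is therefore conditional on cross-over therapy and on 4.15 being followed.

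The obvious repair could also backfire. Excluding SSC-free subjects for any alternative therapy within 90 days, but SSC subjects only for therapy before onset, would on the broad reading drop mainly non-events. With an assumed 25% of ciNPT and 10% of SOC non-events lost, the odds ratio goes from 0.444 to 0.444 × 0.90/0.75 = 0.533. The term must be defined at the same time.

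A reader might infer that the primary result is at risk, or that the rule favours ciNPT. The documents support neither. mITT does not use this exclusion, and more cross-over among SOC events would work against ciNPT.

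**Conclusion.** The point holds, as a minor one. Read as cross-over therapy and with 4.15 followed, the alternative-therapy limb of mPP removes, for cross-over before Day 90, only subjects who already have a primary event. Equal shares lower the rates, the difference and power but leave the odds ratio unchanged; unequal shares bias the odds ratio toward the arm that loses more events. Every share used here is assumed, so the figures show what could happen, not what is likely. The limb does not touch the mITT tests or the PP set.

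**What to change.** In Protocol 8.2 and SAP 5:

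1. State that alternative therapy means cross-over therapy as in Protocol 4.15, that is, therapy of the arm not assigned, and not routine later dressings.
2. State that a subject whose cross-over therapy, or 4.15 procedure such as repeat surgery through the incision, started on or after the onset of the first SSC stays in mPP as an event. Exclude only those whose cross-over or prohibited procedure came before any SSC.
3. In SAP 8.1, report mPP exclusions by arm and by SSC status.

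The cost is a few sentences. SSC onset dates are already recorded (Protocol 4.11.1), and the intervention record, which includes a date, is kept throughout follow-up: "Information related to all interventions that are performed for an SSC will be documented at all post-surgery visits". Protocol 4.10.3.3 names only the type of later dressing, so a start date for cross-over therapy may have to be added. mPP will be closer to PP. An SSC-free cross-over subject who still has a Day 90 assessment would still be dropped as a non-event, which is why item 3 is needed. Treatment, sample size and the primary analysis do not change.
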